### **Risks Associated with Breach of Confidentiality**

There is a risk of breach of confidentiality. Multiple measures will be taken to minimize this risk. All information that could be used to identify a participant will be kept in a secure and locked space accessible only by the trained study coordinator and the principal investigator. All of these documents will be kept in locked file cabinets, in locked offices, at all times. Also kept secure and separate from other files will be the unique ID for each participant. Information collected will be stored on Box Secure Storage or REDCap. The computers used are password-protected and will only be used by trained study staff and for study purposes only. All blood samples are uniquely coded by number and are "de-identified." Blood samples collected to test for biomarkers will be stored behind locked doors in on-site freezers for an indefinite period of time with only coded numbers

as the key to identity. The key to the codes will be available only to selected investigators. Participants wishing to withdraw their samples from the study may do so at any time by notifying the investigators in writing. There is also a small chance that, if participants engage in a videoconference through the Zoom for Healthcare platform, the Zoom session could be hacked.

#### **Participant monitoring**

Study staff will monitor and respond to reports regarding adverse events collected during sessions and on self-report questionnaires. Adverse events will also be assessed once per week throughout the study over the phone and entered into a REDCap form. Participants will also be instructed to contact the investigators and/or study staff if they experience a serious adverse event. If an event occurs, protocols for adverse event classification and reporting will be followed.

#### **Participant confidentiality**

Procedures are in place for maintaining the full confidentiality of all information collected. Participant confidentiality will be protected by securing all hard copy study files in locked filing cabinets. Electronic files containing personal identifiers will be stored on Box Secure Storage or REDCap. All study staff receive training on privacy standards for maintaining participant confidentiality. All published reports will be of summary nature and no individual participants will be identified beyond the investigative staff involved in the project. Electronic data management is described above (see 'Data Coordination').

Reproduction Risks:

#### **Pregnancy**

We are excluding pregnant or lactating people from this study.

Risks to Others: N/A

### **14.0 Potential Benefits to Participants**

Potential Benefits:

Because this study will be used to develop clinical trials for testing pharmacological interventions to treat neuropathic pain in SCI, there is a potential future benefit to the spinal cord population.

### **15.0 Statistical Considerations**

#### *15.1 Data Analysis Plan:*

For Aim 1, the first step for each outcome variable (e.g., pain,) is an unadjusted comparison across the groups as randomized. Each of the outcome variables uses a pre-defined instrument which has both top and bottom boundaries. These bounds are, however, wide enough so that the first steps will ignore the boundaries. The first analysis in each case is an unadjusted analysis and will be done in two ways: (1) a t-test (assuming unequal variances) and (2) a rank-sum test to take advantage of the Mann-Whitney score, which provides the probability that one group will have scores greater (less) than the other group. This statistic is the same as the c statistic widely used after logistic regression. The next step for each outcome is regression model with the main predictor being an indicator group. Standard covariates (e.g., demographics, and measures relevant to SCI such as severity and time since injury) will be included in the analysis. Robust estimator of the standard errors will be used. Predicted values will be checked to see whether any, and, if so, how many, are outside the boundaries of the measure used for that outcome. As a sensitivity analysis, regression models that recognize the boundaries will be used (e.g., fractional logistic regression or two-limit Tobit models). The main analysis will be Intention-to-Treat.

For Aim 2, we will use the same analytic approach we have refined in our 2 active rsfMRI studies and our ongoing task-based and rsfMRI study in adults with SCI and neuropathic pain.

Structural Preprocessing: We will perform preprocessing using the latest containerized fMRI preprocessing pipeline (FMRIPREP) version with standardized Brain Imaging Data Structure (BIDS) formatted Neuroimaging Informatics Technology Initiative (NIFTI) data. Each T1-weighted (T1w) volume will be corrected for intensity non-uniformity (INU) using N4BiasFieldCorrection and skull-stripped using antsBrainExtraction.sh (using the OASIS template). Brain surfaces will be reconstructed using recon-all from FreeSurfer, and the brain mask estimated will be refined with a custom variation of the method to reconcile Advanced Normalization Tools (ANTs)-derived and FreeSurfer-derived segmentations of the cortical gray-matter of Mindboggle. Spatial normalization to the International Consortium for Brain Mapping (ICBM) 152 Nonlinear Asymmetrical template will be performed through non-linear registration with the Registration tool of ANTs using brain-extracted versions of T1w volume and template.

fMRI Preprocessing: We will perform preprocessing with the latest

containerized FMRIPREP85 version with standardized BIDS formatted NIFTI data. Functional data will be slice time corrected using 3dTshift from Analysis of Functional NeuroImages (AFNI) and motion corrected using mcflirt. This is followed by co-registration to the corresponding T1w using boundary-based registration with 9 degrees of freedom, using bbrregister (FreeSurfer). Motion correcting transformations, field distortion correcting warp, BOLD-to-T1w transformation and T1w-to-template (Montreal Neurological Institute, MNI) warp will be concatenated and applied in a single step using antsApplyTransforms (ANTs v2.1.0) using Lanczos interpolation. Physiological noise regressors will be extracted by applying CompCor. Principal components will be estimated for the two CompCor variants: temporal (tCompCor) and anatomical (aCompCor). Framewise displacement and DVARS90 will be calculated for each functional run using the implementation of Nipype. Independent Component Analysis (ICA)-based Automatic Removal Of Motion Artifacts (AROMA) will be used to generate aggressive noise regressors and to create a variant of data that is non-aggressively denoised.

For Aim 3, we will analyze miRNA expression profiles for raw cycle threshold (Ct) values using real-time Statminer software (Integromics, Inc) to identify significantly altered miRNAs. For relative quantification of miRNAs between placebo and brivaracetam-treated samples, the following steps will be performed in the Statminer software suite: quality control of biological replicates, filtering of miRNAs expression having Ct values below cycles and the detection of expression in all biological replicates of calibrator and target. Statistically significant miRNAs will be selected based on stringent parameters such as Benjamin-Hochberg FDR and data will be conservatively selected with adjusted p-values and p-value lower than 0.01 and 0.05, respectively. Functional pathway analysis of altered miRNAs and their association with genes related to reduction in neuropathic pain will be performed using Ingenuity Pathway Analysis (IPA) program (Ingenuity Systems Inc., Redwood City, CA). For clinical correlation analysis, data comparing changes in miRNA expression will be described as means with standard error of the mean. To analyze the differences between group means we will use analysis of variance after assessing for distribution and variance. We will use Games-Howell test for multiple comparisons.

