### **3.0 Study Endpoints/Events/Outcomes**

Primary Endpoint/Event/Outcome:

Our primary endpoint will be reduction in pain intensity assessed by the International Spinal Cord Injury Pain Data Set.

Secondary Endpoint(s)/Event(s)/Outcome(s):

Secondary outcomes include brain resting state and task based activity and functional connectivity and various psychosocial factors related to participants' experiences with SCI, such as change in mood, satisfaction with life, community integration, sleep, self-efficacy, pain catastrophizing, perceived disability, and spasm frequency.

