Once randomized, the 7-week supply of study drug will be dispensed and mailed directly to participants to begin 7 weeks of active treatment or placebo, as described in Section 4.0. All participants will receive a medication diary to track study drug compliance and to record medication use.

Weekly phone check-in: Masked data collectors will perform weekly check-in calls to assess for medication-related adverse events (AEs). The data collector will also administer the Patient Health Questionnaire 9-item (PHQ-9) to assess for changes in mood and suicidality. A suicide protocol will be initiated if a participant endorses suicidality (see below). Participants will also report on their level of pain (rate highest, lowest, and average pain (0-10) that day). Reported AEs identified in these calls will be documented and immediately shared with the PI for review.

Suicide Protocol: Endorsement of active suicidality on PHQ-9 will trigger the suicide protocol. Study staff will call 911 in the event of a psychological emergency noted during a phone call (credible report of intent to harm oneself). Study staff will first ask to speak to another adult in the household. If none is present or comes to call, study staff will call 911 and remain on the line until first responders arrive. In the event of a non-emergent psychological situation (psychological distress in the absence of intent for self-harm), study staff will refer the participant to their PCP or the National Suicide Hotline ([name]). In either case, study staff will notify the PI immediately.

Visit 3: End of intervention assessments will be repeated 5 weeks after Visit 2. This includes a focused physical exam, a mental health and health history screen, optional blood draw, optional MRI, and questionnaires relating to pain, mood, active suicidality, satisfaction with life, kinesiophobia, sleep quality, and community integration. Additionally, limited safety labs will be repeated (from pre-Visit 1) to confirm normal renal function, absence of liver cirrhosis, and absence of pregnancy in individuals of childbearing potential. The fasting blood draw and analysis

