### 15.3 Statistical Analysis:

All statistical analyses will be conducted with Stata v. 17.0 or SAS v.9.4.72 assuming a 5% level of significance unless otherwise stated. Participant characteristics will be described using frequency counts and percentages (nominal variables) and means/standard deviations (SDs) or medians and interquartile ranges (IQRs) (continuous variables). Chi-square tests and t-tests or rank-sum tests will be used to compare the subject characteristics between the treatment arms.

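### Aim 1 names no primary test, leaves the outcome as change or Visit 3 score, and does not name baseline pain as a covariate; one baseline-adjusted ANCOVA would settle all three

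*Combined protocol and SAP*

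**What the plan says.** Section 3.0 defines the endpoint: "Our primary endpoint will be reduction in pain intensity assessed by the International Spinal Cord Injury Pain Data Set". It attaches no test to it. Section 15.2 bases power on the between-arm difference in pre-post change, two-sided at 0.05, and also names no test.

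Section 15.1 sets out the Aim 1 analysis in order:

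- "The first analysis in each case is an unadjusted analysis and will be done in two ways": a t-test with unequal variances and a rank-sum test.
- "The next step for each outcome is regression model with the main predictor being an indicator group". On covariates: "Standard covariates (e.g., demographics, and measures relevant to SCI such as severity and time since injury) will be included in the analysis". On standard errors: "Robust estimator of the standard errors will be used", with the type not given.
- Models that respect the scale limits (fractional logistic, two-limit Tobit), labelled as sensitivity analysis.
- "The main analysis will be Intention-to-Treat". This fixes the analysis set, not the test.

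Section 15.3 covers all analyses, "assuming a 5% level of significance unless otherwise stated".

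Pain questionnaires are given at Visit 1 and Visit 3 (Section 5.0 and Table 1). Section 5.0 describes the International SCI Pain Data Set as rating average pain over the last week from 0 to 10.

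**The concern.** Three choices are left open: which test decides Aim 1, whether it is applied to change or to the Visit 3 score, and which covariates enter the regression. Each can move a p-value across 0.05 in a trial of about 40 completers. If they are settled after the data are seen, a nominal 5% test no longer has a 5% error rate.

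The second issue is efficiency. Pain on the same scale before treatment is available at no extra cost, and using it as a covariate removes noise from the arm comparison. The section names demographics, severity and time since injury, but not baseline pain. With 20 per arm the precision lost is not trivial.

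**Working it through.** **Inputs.** From Section 15.2: n = 20 per arm, difference δ = 2 points, SD = 3.17 (28 adults, mean 3.43), two-sided α = 0.05. This SD describes pain intensity at one time, not change. The pre-post correlation r is not given, so a range is shown.

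**The plan's own figure.** Section 15.2 claims more than 80% power. For two arms with SD 3.17, the noncentrality is δ / (SD × √(2/n)) = 2 / (3.17 × 0.316) = 1.995. On 38 degrees of freedom the critical value is 2.024 and power is 49.4%. The stated figure is reached only if the SD of change is about 2.2, which corresponds to r of about 0.75 (normal approximation, 80.6%) or 0.76 (t distribution, 80.1%). The section states no such value.

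**Power by method.** The SDs that drive the comparison are:

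- Visit 3 score, unadjusted: 3.17
- Change score: 3.17 × √(2(1 − r))
- ANCOVA on baseline: 3.17 × √(1 − r²)

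| r (assumed) | Change SD | ANCOVA SD | Power, Visit 3 score | Power, change | Power, ANCOVA |
|---|---|---|---|---|---|
| 0.3 | 3.75 | 3.02 | 49.4% | 37.6% | 53.1% |
| 0.5 | 3.17 | 2.75 | 49.4% | 49.4% | 61.2% |
| 0.6 | 2.84 | 2.54 | 49.4% | 58.5% | 68.1% |
| 0.7 | 2.46 | 2.26 | 49.4% | 70.9% | 77.7% |
| 0.75 | 2.24 | 2.10 | 49.4% | 78.5% | 83.6% |

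The ordering is general. Since 1 − r² = (1 − r)(1 + r) and 1 + r is at most 2, the ANCOVA SD never exceeds the change SD. It also never exceeds 3.17. The ANCOVA column ignores the cost of estimating the baseline slope. With n = 20 that adds about 1/(2n − 4) = 1/36, or 2.8%, to the variance and uses one degree of freedom, which lowers power by about one point (60.0% at r = 0.5, 76.5% at r = 0.7).

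**Baseline imbalance.** The standard error of a chance arm difference in baseline pain is 3.17 × √(2/20) = 1.0 point. The trial enrols only pain grades 3 to 10 (Section 8.0), so the spread may be smaller. A uniform spread over the integers 3 to 10 has SD √((8² − 1)/12) = 2.29 and standard error 2.29 × √(2/20) = 0.72.

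**False-positive rate if any p<0.05 counts.** Null trials were simulated, 8,000 per scenario, with 20 per arm on a 0-10 scale. The regression had two to six covariates explaining 0 to 30% of the variance and HC1 or HC3 robust errors. These settings are assumptions.

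- Two unadjusted tests only: 5.4-6.2%.
- With the regression added: 7.2-9.0%. With four covariates explaining 15% and HC1 errors it was 8.4% on change and 8.0% on the Visit 3 score.
- If change versus Visit 3 score is also left open: 13-16%.
- A single ANCOVA on baseline: 5.0-5.5%.

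The simulation error on 8% is √(0.08 × 0.92/8,000) = 0.3 percentage points.

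**The case against.** Section 15.1 is not a free-for-all. It orders the steps, calls only two tests the first analysis, places the regression after them, and labels the boundary models as sensitivity analysis. A reader might infer three equal primary tests and hence an 8% error rate. The text does not support that: the first two tests alone give about 6%, and 8% needs both the regression as an equal third route and a rule that any significant result is success. The plan states no such rule.

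A reader might also infer that baseline pain is ignored or excluded. It is not. The covariate list is given by example and is open, and Sections 3.0 and 15.2 point to a change outcome, which uses baseline by subtraction. If change is analysed, a chance baseline difference is partly dealt with; it goes wholly uncorrected only in an unadjusted Visit 3 comparison. What stands is that Section 15.1 does not say which outcome applies, and that an open list is unspecified.

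The size of the gain depends on r. If the plan's power claim is taken at face value, r is about 0.75 and ANCOVA gains about 5 points over change, not 12. The low absolute power at r = 0.5 mainly reflects the sample-size calculation, which is a separate matter.

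The weekly calls ("Participants will also report on their level of pain (rate highest, lowest, and average pain (0-10) that day") are same-day ratings. They are neither the Visit 1 baseline nor the last-week average, so they do not fill the gap.

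Finally, Sections 2.2 and 18.2 call this a pilot. That lowers the severity. It does not remove the need for a named test, since Section 1.1 sets out to determine efficacy and Section 15.2 powers a significance test.

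**Conclusion.** The point holds as a specification gap with a free improvement attached. No section says which Aim 1 result decides the primary endpoint or in what form the outcome is analysed, and baseline pain is unnamed.

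The gain in power from ANCOVA over a change-score t-test is 61.2 − 49.4 = 11.8 points at r = 0.5, 6.8 at r = 0.7 and 5.1 at r = 0.75. Over an unadjusted Visit 3 comparison it is 11.8 points at r = 0.5 and 34.2 at r = 0.75. These figures assume SD 3.17 at both visits and an r that the documents do not supply, and they are about one point generous to ANCOVA.

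The false-positive exposure of about 6% (two tests) or 7-9% (three) is conditional on picking any significant result. It bounds what the wording permits and does not predict what will be done. Choosing ANCOVA over a change score is a matter of efficiency; a pre-named change-score test would be valid. The change should be made, but it does not invalidate the design.

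**What to change.** In Section 15.1, name one primary analysis: regression (ANCOVA) of Visit 3 average pain on the International SCI Pain Data Set (0-10) on arm and Visit 1 pain on the same scale, in the intention-to-treat set, two-sided 5%, reported with a 95% confidence interval. State the type of robust standard error if one is used.

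Label the unequal-variance t-test, the rank-sum test and the fuller covariate regression as supportive, and keep the boundary models as sensitivity analyses. List the covariates of the fuller regression in full. Adjust each secondary scale for its own baseline.

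Because Section 10.0 expects 20% attrition and Section 15 gives no method for missing outcomes, the same paragraph should say how participants without Visit 3 pain enter the intention-to-treat analysis.

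The cost is a wording amendment, made before unblinding. It needs no extra participants and no visits or instruments beyond the pain assessments already scheduled at Visits 1 and 3. Settling the missing-data method needs some thought beyond wording.

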#### Specific Aims:

**Specific Aim 1: Determine whether a 7-week course of daily brivaracetam reduces below-level neuropathic pain in SCI.** The objective of this aim is to assess efficacy of a 7-week course of brivaracetam to reduce neuropathic pain in men and women with SCI. We will assess change in pain intensity and related outcomes, including mood, satisfaction with life, and community integration. We will monitor drug adverse events and tolerability.

**Specific Aim 2: Determine whether a 7-week course of daily brivaracetam increases parietal operculum brain connectivity.** The objective of this exploratory aim is to assess the effect of a 7-week course of brivaracetam treatment on parietal operculum activation and connectivity in SCI. We will assess changes in cortical activity of related pain perception regions and networks in the brain in response to brivaracetam treatment compared to placebo using rsfMRI and pain-related task-based fMRI. To achieve this aim, we will test the working hypothesis that brivaracetam increases parietal operculum activation and connectivity compared to placebo, using rsfMRI, task-based fMRI, and a validated image processing protocol. We will also examine changes in network connectivity and brain activity in the insula, because of its concurrent reported importance for neuropathic pain in SCI. We will assess the association between functional connectivity of the parietal operculum and the insula and change in pain intensity in response to brivaracetam treatment.

**Specific Aim 3: Determine whether baseline microRNA-485 levels are associated with response to brivaracetam treatment.** The objective of this exploratory aim is to assess microRNA expression as a potential predictive biomarker of response to brivaracetam treatment. To achieve this, we will test the working hypothesis that baseline circulating miR-485 levels predict change in pain intensity in response to brivaracetam treatment. To test this, we will use Next-Generation sequencing. We will assess miR-485 levels at baseline and after a three-month treatment course.

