The study of miRNA in neuropathic pain is a relatively new field of research. However, the significance of miRNA alterations in a variety of rodent pain models and in clinical conditions characterized by pain has been clearly established (there are more than 30 publications in 2019 alone). The majority of these studies have been conducted in animal models. However, a few studies also describe changes in miRNAs-signatures in complex regional pain syndrome [Orlova et al., 2011] and irritable bowel syndrome-patients [Zhou et al., 2010]. There is evidence that a specific miRNA might play a role in the pathogenesis of neuropathic pain in SCI. miR-485 regulates presynaptic expression of SV2A and regulates dendritic spine density and synapse morphology and function [Cohen et al., 2011]. Synaptic plasticity is a homeostatic response essential to adapt neural circuit connectivity and excitation in response to neurotrauma. miRNA-485 expression is regulated in a number of neurological diseases and after brain trauma. For instance, miRNA-485 is down-regulated in Huntington disease [Packer et al., 2008], Alzheimer's disease [Cogswell et al., 2008], and traumatic brain injury [Redell et al., 2009]. These disease studies, together with our findings that SV2A

expression is increased in individuals with neuropathic pain, suggest that decreased levels of miR-485 with corresponding increased levels of SV2A and neural network activity in nociceptive neurons may contribute to the pathophysiology of SCI-induced neuropathic pain.

Because miR-485 regulates SV2A expression, the target of brivaracetam, we hypothesize that circulating miR-485 may be a valuable predictive biomarker of response to therapy. That is, we hypothesize that individuals with lower circulating miR485 levels may be less likely to respond to brivaracetam treatment for neuropathic pain than those with higher circulating miR485.

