Screening: A phone screen will be administered to confirm basic eligibility criteria listed in Section 8.1 such as age, pain level, medication use, and other medical conditions. Study staff will also screen for MRI contraindications at that time with the Center for Magnetic Resonance Research (CMRR) pre-screening questionnaire (i.e., implanted medical devices or retained metal fragments). Eligible individuals will be required to receive medical clearance from their primary care provider within one month of (prior to) Visit 1, including physical exam, health history, and lab work to confirm normal renal function, absence of liver cirrhosis, and absence of pregnancy. While we will target obtaining lab work within 1 month of baseline, labs up to 6-weeks prior to baseline will be accepted to reduce participant burden. Their insurance will be charged, and they will be responsible for any associated copays or costs.

For participants who recently had comprehensive metabolic panel done, medical record review of lab results can replace new screening labs if the blood labs were completed within one month of (prior to) the scheduled baseline appointment. If the participant is seeing a provider in-system, the study coordinator will pull labs from the medical record. If the participant is not seeing a provider in-system, the study coordinator will instruct the participant's physician to fax the lab report to the study coordinator. The instructions for faxing will be on the screening eligibility sheet the participant brings to their doctor's appointment and available to be emailed for the participant upon request.

Visit 1: This visit includes informed consent, randomization, a focused physical exam, and a mental health and health history screen. CDE-recommended questionnaires relating to pain, mood, active suicidality, satisfaction with life, kinesiophobia, sleep quality, and community integration will also be administered.

Visit 2: This visit may be combined with Visit 1, if the participant prefers. Visit 2 includes an optional blood draw for batch analysis and an optional MRI scan; the optional MRI and optional blood draw are paid for by the study. Visits 1 and 2 can take place either at the study site or virtually, depending on participant preference. Those who choose to participate in the study virtually will not take part in the MRI or blood draw. For participants with contraindications to MRI, the MRI will not be completed.

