### 15.2 Power Analysis:

We present power and sample size analysis for the primary endpoint; a 2-point improvement in neuropathic pain intensity as assessed by the

International Spinal Cord Injury Pain Basic Dataset. We based our sample size calculation on variations in pain intensity observed in an ongoing clinical trial (DoD W81XWH-14-SCIRP-CTA, [name] PI). In this sample, average neuropathic pain intensity in 28 adults with SCI was  $3.43 \pm 3.17$ . Based on this, a sample size of 20 per arm will have more than 80% power to detect a significant difference in pre-post changes of neurological pain between the two arms at a two-sided significance  $\alpha$  level of 0.05. This sample size is sufficient to address the exploratory analyses proposed in Aims 2-3.

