16.6 Consultants. Vendors. Third Parties: -

*LC Sciences*

We will send blood serum samples to LC Sciences (Houston, TX) to perform microRNA analysis (non-genomic analysis). LC Sciences will have access to de-identified data only.

*REDCap eConsent*

The informed consent form and HIPAA form will be signed with an eSignature using REDCap. The REDCap eConsent process is a 21 CFR Part 11 compliant method for electronic signature capture. For more information on REDCap compliance, please visit:

[https://redcap.ahc.umn.edu/surveys/?s=3PT9FY73NC&topics\\_\\_\\_ec=1#ec](https://redcap.ahc.umn.edu/surveys/?s=3PT9FY73NC&topics___ec=1#ec)

Links to identifiable data:

The research data will be collected on RedCap and on the MRI. Those data will not contain personal identifiable information. Only the PIs and designated study staff will have a document that links the name with the code, which will be kept secure on the University Box secure storage.

Sharing of Data with Research Team Members:

Only deidentified data will be shared with team members. The PIs and clinical trial coordinators will have access to identifiable information for contact purposes.

Storage and Disposal of Paper Documents:

Documents will be stored in a secure closet behind secure doors in the PI and Co-PI's offices and labs. Documents that need to be disposed will be disposed of in secure bins and then shredded.

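### No analysis in Section 15 relates baseline miR-485 to pain change, which is what exploratory Aim 3 sets out to test, and the planned Ct steps do not fit the sequencing assay that Aim 3 names

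*Combined protocol and SAP*

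**What the plan says.** The Specific Aims state the Aim 3 hypothesis: "we will test the working hypothesis that baseline circulating miR-485 levels predict change in pain intensity in response to brivaracetam treatment". Section 2.3 gives it a direction, that "individuals with lower circulating miR485 levels may be less likely to respond to brivaracetam treatment". The assay is named in the same aim: "To test this, we will use Next-Generation sequencing".

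The Aim 3 paragraph of Section 15.1 is the only analysis text for this aim. It begins: "we will analyze miRNA expression profiles for raw cycle threshold (Ct) values using real-time Statminer software". It goes on: "For relative quantification of miRNAs between placebo and brivaracetam-treated samples, the following steps will be performed in the Statminer software suite". Selection of altered miRNAs by false discovery rate follows, then pathway annotation. A step labelled as clinical correlation then summarises changes in miRNA expression as means with standard errors and compares group means by ANOVA with Games-Howell.

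On numbers, Section 15.2 says: "This sample size is sufficient to address the exploratory analyses proposed in Aims 2-3". Section 5.0 makes the biomarker sample voluntary: "Visit 2 includes an optional blood draw for batch analysis and an optional MRI scan". Participants who take part entirely remotely give no banked blood.

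**The concern.** The hypothesis needs the baseline marker on the right-hand side of a model and pain on the left. The planned screen and the planned ANOVA both put miRNA on the left. They would show whether the drug alters miRNA levels, which is a different question from whether miR-485 before treatment identifies who benefits.

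The background presents miR-485 as a predictive biomarker of response to this drug. An association seen only in treated participants cannot separate that from a marker of prognosis under any treatment. The placebo arm makes the distinction possible, but no arm-by-marker term is planned.

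The plan says that the pilot's results will be used to design larger trials. Without a stated model, any miR-485 result carried forward would depend on analysis choices made after the data were seen. Separately, Ct values come from PCR and sequencing yields read counts, so the written processing cannot be run on the assay that the aim names.

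**Working it through.** **1. Is the hypothesis tested anywhere in Section 15?** Each analysis was set against what Aim 3 needs: baseline miR-485 as predictor and participant-level pain as outcome.

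- Section 15.1, Aim 1: tests between arms, then regression on a group indicator with demographic and injury covariates. No miRNA.
- Section 15.1, Aim 3 screen: miRNA is the outcome and arm is the contrast. No pain variable.
- Section 15.1, Aim 3 pathway step: links miRNAs to genes associated with pain relief. This is gene annotation and does not use participants' pain scores.
- Section 15.1, Aim 3 clinical correlation step: outcome is change in miRNA, and the groups are not defined. Neither pain nor a baseline level is mentioned.
- Section 15.2: power for the primary endpoint only.
- Section 15.3: descriptive comparisons, and for Aim 2 Pearson correlations of brain-function change with sensory and motor measures. No miRNA.

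Section 15 never names miR-485, and none of these analyses has the required form.

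**2. Do the assay and the processing agree?** The Specific Aims name sequencing; Section 15.1 filters and quantifies Ct values. Section 16.6 names the laboratory that will run the microRNA analysis but not the platform, so it does not settle the matter.

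**3. What could the sample size detect?** The plan gives no Aim 3 figure to reproduce. Inputs for an approximation:

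- 20 per arm (Section 15.2).
- Two-sided alpha 0.05 (stated in Section 15.2 for the primary endpoint; assumed here for Aim 3).
- 80% power (assumed). The multiplier is 1.960 + 0.842 = 2.802.
- 10 per arm is an illustrative assumption, as if half skip the optional draw. The documents give no expected uptake.

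Within the active arm, the smallest detectable correlation is r = tanh(2.802/√(n − 3)):

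- n = 20: tanh(2.802/√17) = tanh(0.680) = 0.59
- n = 10: tanh(2.802/√7) = tanh(1.059) = 0.79

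For a contrast between arms with zero correlation in placebo, the active-arm value must reach r = tanh(2.802 × √(2/(n − 3))), with n per arm:

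- n = 20: tanh(2.802 × √(2/17)) = tanh(0.961) = 0.74
- n = 10: tanh(2.802 × √(2/7)) = tanh(1.498) = 0.90

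Power for 0.5 versus 0 is Φ(atanh(0.5)/√(2/(n − 3)) − 1.960). With 20 per arm this is Φ(0.549/0.343 − 1.960) = Φ(−0.36), about 36%. With 10 per arm it is Φ(0.549/0.535 − 1.960) = Φ(−0.93), about 18%.

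These figures concern correlations. A regression interaction compares slopes and is adjusted for baseline pain, so they are a guide to its sensitivity and not an exact power calculation.

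**The case against.** The strongest defence is proportion. Aim 3 is labelled exploratory, the trial is described as a pilot, and miRNA is in neither list of secondary outcomes (Sections 3.0 and 5.0). That stands, and it limits the consequence. It does not supply the missing analysis.

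The undefined ANOVA groups might be meant as responder categories. Games-Howell is a multiple-comparison procedure and adds little with two groups, so something other than the two arms may be intended. A reader might therefore go too far in concluding that the authors meant pain to play no part. What can be said is that the text does not define such groups and that it concerns change in miRNA, not the baseline level.

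A reader might also infer that the broad screen is itself a mistake, because multiplicity correction is spent on many markers when one was named in advance. The documents do not support this. Section 2.3 makes miRNA signatures a goal of the project, no number of markers is given, and FDR control within a screen would not penalise a separate test of miR-485.

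The headline of Aim 3 speaks of association with response, which an analysis within the active arm would address. The interaction is the stricter test and has low power here. This is a fair point, and it is a reason to report both.

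Finally, it is tempting to treat sequencing as right and the Ct text as stale. The documents only conflict; either passage could be the outdated one.

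**Conclusion.** The concern holds for Aim 3. As written, the plan contains no test of whether baseline miR-485 predicts pain change, and its processing steps contradict the assay named in the aim. Both conclusions rest on the text alone.

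The sufficiency statement in Section 15.2 has no calculation behind it for this aim. Under the approximation above, 20 participants per arm with blood would detect only large effects, and fewer samples would require larger ones still. The 10-per-arm results depend on the assumed uptake. A reader might extend these figures to the imaging analyses of Aim 2, which the same sentence covers. They do not apply there, because no imaging effect was calculated.

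A reader might also take the gap as a threat to the trial's main result. It is not: the primary pain comparison does not use miRNA.

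**What to change.** 1. **Section 15.1.** Add a pre-specified Aim 3 analysis, labelled exploratory. Regress Visit 3 pain intensity on arm, baseline pain, baseline miR-485 (log scale, normalised for the assay used) and arm-by-miR-485. Report the interaction and the association within the active arm, each with a 95% confidence interval. With baseline pain in the model, using pain change as the outcome gives the same arm, marker and interaction coefficients, so this matches the hypothesis. Keep the all-miRNA comparison between arms as a separate FDR-controlled screen. If the ANOVA stays, define its groups.

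2. **Specific Aims and Section 15.1.** State one assay in both places and match the processing and model to it: count-based for sequencing, Ct-based for PCR.

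3. **Section 15.2.** Remove the claim of sufficiency for Aim 3. Alternatively, replace it with approximate detectable effects for miR-485 under a stated assumption about uptake of the optional draw. Do not apply those figures to Aim 2.

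The cost is wording. The samples and pain scores needed are already planned, and the change should be made before any unblinded analysis. The downside is that the stated adequacy for Aim 3 becomes less favourable.
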